5.1 Inclusion criteria

Participants eligible for inclusion in this study must meet **all** of the following criteria:

1. Male and female patients aged ≥ 18 years at screening
2. Signed Informed Consent Form (ICF) by patient capable of giving consent, or, when the patient is not capable of giving consent, by his or her legal/authorized representative (if allowed according to local requirements)
3. Clinically diagnosed with the SARS-CoV-2 virus by polymerase chain reaction (PCR) or by other approved diagnostic methodology within 7 days prior to randomization

4. Hospitalized with COVID-19-induced pneumonia evidenced by chest x-ray, computed tomography scan (CT scan) or magnetic resonance scan (MR scan) (taken within 5 days prior to randomization)
5. Impaired respiratory function, defined as peripheral oxygen saturation (SpO_2) $\leq 93\%$ on room air or partial pressure of oxygen (PaO_2) / fraction of inspired oxygen (FiO_2) <300 millimeter of mercury (mmHg) at time of screening For cities located at altitudes greater than 2500 m above sea level, these will be substituted with $\text{SpO}_2 <90\%$ and $\text{PaO}_2/\text{FiO}_2 <250$ mmHg
6. Acute Physiologic Assessment and Chronic Health Evaluation (APACHE) II score of ≥ 10 at time of screening
7. CRP ≥ 20 mg/L or ferritin level ≥ 600 $\mu\text{g}/\text{L}$ at screening
8. Body weight between 45 kg and 145 kg, inclusive, at screening
9. Ability to comply with the study protocol, in the investigator's judgment

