3. **Follow-up** (Day 16-29): After completion of the treatment period, patients will be observed until Day 29 or discharged from hospital, whichever is sooner. Study assessments to be conducted every 2 days for domiciled patients.
If patients are discharged from hospital prior to Day 29, a study visit conducted by telephone will occur on Day 29 (all other visits between discharge and Day 29 can be omitted).
4. **Safety follow-up visit assessment** (Day 45): A follow-up visit will be conducted at Day 45 if the patient is hospitalized. If patients are discharged from hospital prior to Day 45, a study visit will be conducted by telephone on Day 45.
5. **End of Study/Safety follow-up visit assessment** (Day 127): A follow-up visit for safety will be conducted at Day 127 if the patient is hospitalized. If patients are discharged from hospital prior to Day 127, a study visit will be conducted by telephone on Day 127.

2 First interpretable results (FIR)

Commercially Confidential Information

Commercially Confidential Information

3 Interim analyses

Commercially Confidential Information

4 Statistical methods: Analysis sets

For all analysis sets, participants will be analyzed according to the study treatment(s) randomized.

The Safety analysis set will include all randomized participants that have received any study drug.

Commercially Confidential Information

The PD analysis set will include all randomized participants with no protocol deviations with relevant impact on PD data.

The PD analysis set 2 will include all randomized participants with no protocol deviations with relevant impact on PD data. The participants that did not meet all the eligibility criteria mentioned in study protocol section 5 will be excluded from this set programmatically. Exclude participants with APACHE II score less than 10 at baseline programmatically.

The analysis sets and protocol deviation codes are related as follows:

Table 4-1 Protocol deviation codes and analysis sets

Category Deviation code	Text description of deviation	Data exclusion
	Subjects are excluded from safety analysis in case of these PDs:	Exclude subject from safety analysis set
INCL02	Informed consent form not obtained	Yes

Commercially Confidential Information

Category Deviation code	Text description of deviation	Data exclusion
	Subjects are excluded from safety analysis in case of these PDs:	Exclude subject from safety analysis set
INCL02	Informed consent form not obtained	Yes

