10.2 APACHE II

The APACHE II score is derived from a number of different clinical endpoints according to the scoring table as outlined in ([Knaus et al., 1985](#)):

1. Body temperature (°C)

Depending on the collection method selected apply the following correction factors before scoring:

- Core: no correction needed
- Axillary: + 1.0 °C
- Oral: + 0.5 °C
- No method selected: no correction.

2. Mean Arterial Pressure (mmHg)

In case the “method” is reported as “calculated” confirm the calculation by applying the following formula: $\text{MAP} = [\text{SBP} + (2 \times \text{DBP})] / 3$. If the reported and recalculated numbers differ by more than 10% use the recalculated value (i.e. if reported value < 0.9* recalculated value or reported value > 1.1* recalculated value)

3. Heart Rate (beats per minute)

If the participant has a pacemaker any HR ≤ 109 bpm will be scored to 0.

4. Respiratory Rate (breaths per minute)

5. Oxygenation: depending on the Fraction of inspired Oxygen (FiO2, where FiO2 is a value between 0 and 1 (i.e. not on % scale)):

- a. If $\text{FiO}_2 < 0.5$: use PaO_2 (mmHg)

- b. If $\text{FiO}_2 \geq 0.5$: use A-aDO_2 (mmHg): where A-aDO_2 is calculated as $\text{A-aDO}_2 = (\text{FiO}_2 \times 713 - \text{PaCO}_2/0.8) - \text{PaO}_2$

In case PaO2 is not available for a certain visit it can be derived from SPO2 if available instead using the following conversion table:

Table 10-1Conversion of SpO2 to PaO2

SpO2 (%)	PaO2 (mmHg)
80	44
81	45
82	46
83	47
84	49
85	50
86	52
87	53
88	55
89	57
90	60
91	62
92	65
93	69
94	73
95	79
96	86
97	96
98	112
99	145

In case PaCO2 is not available for a certain visit it can be derived from HCO3 if available instead using the following conversion:

$$\text{PaCO2 (mmHg)} = \text{HCO3(mEq/L)} * 1.5 + 8$$

6. Arterial pH: if Arterial pH is not available use Serum HCO3 (venous mMol/L) instead
7. Serum Sodium (mmol/L)
8. Serum Potassium (mmol/L)
9. Serum Creatinine (mg/dL=mg/100mL)
10. Hematocrit (%)

11. White Blood Count ($10^9/\text{L} = 1000/\text{mm}^3 = 10^3/\text{mm}^3$)

12. Age at screening (years)

13. Chronic Health Points at Screening:

Points are assigned only if for this patient “Did the subject experience Severe organ system insufficiency or is immunocompromised ?” is selected as “yes”.

- If “Did the subject experience Severe organ system insufficiency or is immunocompromised ?” = “no”, no points are assigned and a record should not be created for this question in the SDTM data set.

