- If “Did the subject experience Severe organ system insufficiency or is immunocompromised ?” is selected as “yes” Chronic Health points will be derived from “Admission Classification”:
 - Medical(non-operative)
 - Emergency post-operative
 - Elective post-operative

If in this scenario none of these conditions is selected the Chronic Health points will be set to 0.

14. Glasgow Coma Score: First each sub-score is scored according to the scoring table below

- Best Eye Response
- Motor Response
- Verbal Response

Then these three subscores are added up to obtain the scoring of the “Total Glasgow Coma Score”. The value included in the APACHE II for Glasgow-Coma-Score is then = 15 – “Total Glasgow Coma Score”.

SDTM Mapping strategy

APACHE II specific mapping strategy: It provides guidance on how the result variables (RSORRES, RSSTRESC, and RSSTRESN) should be populated for the measure. All original results are represented with preferred terminology in RSORRES. This result is then transformed into a standard numeric score in RSSTRESN and a character representation of the standard numeric score in RSSTRESC.

To obtain the total APACHE II score all 14 derived values of RSSTRESN are then added up. If one item is missing the APACHE II score at SDTM level for this visit is missing. Missing data imputation will be implemented at ADAM level.

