10.2.1 APACHE II Scoring

Temperature (°C)

RSORRES	RSSTRESC	RSSTRESN
>=41	4	4
39-40.9	3	3
38.5-38.9	1	1
36-38.4	0	0
34-35.9	1	1
32-33.9	2	2
30-31.9	3	3
≤29.9	4	4

Mean Arterial Pressure (mmHg)

RSORRES	RSSTRESC	RSSTRESN
>=160	4	4
130-159	3	3
110-129	2	2
70-109	0	0
50-69	2	2
≤49	4	4

Heart rate (BEATS/MIN)

Does the participant have a pacemaker?	RSORRES	RSSTRESC	RSSTRESN
Irrespective	>=180	4	4
Irrespective	140-179	3	3
Irrespective	110-139	2	2
No/unknown	70-109	0	0
No/unknown	55-69	2	2
No/unknown	40-54	3	3
No/unknown	≤39	4	4
Yes	≤109	0	0

Respiratory rate (BREATHS/MIN)

Note: Ventilated or non-ventilated patient scores will be the same as per table below

RSORRES	RSSTRESC	RSSTRESN
>=50	4	4
35-49	3	3
25-34	1	1
12-24	0	0
10-11	1	1

6-9	2	2
<=5	4	4

Impute the unit for respiratory rate as breaths/min in case it is missing.Oxygenation:

- If $\text{FiO}_2 \geq 0.5$ then use A-aDO₂ (mmHg)

RSORRES	RSSTRESC	RSSTRESN
>=500	4	4
350-499	3	3
200-349	2	2
<200	0	0

- If $\text{FiO}_2 < 0.5$ then use PaO₂ (mmHg)

RSORRES	RSSTRESC	RSSTRESN
>70	0	0
61-70	1	1
55-60	3	3
<55	4	4

If any value for <X, impute the value X in that case.

Arterial pH

- Use arterial pH if reported

RSORRES	RSSTRESC	RSSTRESN
>=7.7	4	4
7.6-7.69	3	3
7.5-7.59	1	1
7.33-7.49	0	0
7.25-7.32	2	2
7.15-7.24	3	3
<7.15	4	4

- Alternatively use Serum HCO₃ (mmol/L)

RSORRES	RSSTRESC	RSSTRESN
>=52	4	4
41-51.9	3	3
32-40.9	1	1
22-31.9	0	0
18-21.9	2	2
15-17.9	3	3
<15	4	4

Serum sodium (mmol/L)

RSORRES	RSSTRESC	RSSTRESN
>=180	4	4
160-179	3	3
155-159	2	2
150-154	1	1
130-149	0	0
120-129	2	2
111-119	3	3
<=110	4	4

Serum potassium (mmol/L)

RSORRES	RSSTRESC	RSSTRESN
>=7	4	4
6-6.9	3	3
5.5-5.9	1	1
3.5-5.4	0	0
3-3.4	1	1
2.5-2.9	2	2
<2.5	4	4

Serum creatinine (mg/dL)

RSORRES	RSSTRESC	RSSTRESN
>=3.5 and acute renal failure ="yes"	8	8
2-3.4 and acute renal failure ="yes"	6	6
1.5-1.9 and acute renal failure="yes"	4	4
0.6-1.4 and acute renal failure ="yes"	0	0
<0.6 and acute renal failure ="yes"	4	4
>=3.5	4	4
2-3.4	3	3
1.5-1.9	2	2
0.6-1.4	0	0
<0.6	2	2

Hematocrit (%)

RSORRES	RSSTRESC	RSSTRESN
>=60	4	4
50-59.9	2	2

46-49.9	1	1
30-45.9	0	0
20-29.9	2	2
<20	4	4

White Blood Count ($10^9/L$)

RSORRES	RSSTRESC	RSSTRESN
≥ 40	4	4
20-39.9	2	2
15-19.9	1	1
3-14.9	0	0
1-2.9	2	2
<1	4	4

Age points (years)

RSORRES	RSSTRESC	RSSTRESN
≤ 44	0	0
45-54	2	2
55-64	3	3
65-74	5	5
≥ 75	6	6

Chronic health points

RSORRES	RSSTRESC	RSSTRESN
For non-operative or emergency post-operative patients	5	5
For elective post-operative patients	2	2

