None selected	0	0

Commercially Confidential Information

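### SAP 10.2 scores chronic health as 0 when the condition is recorded as present but the admission class is blank, although every actual class carries 5 or 2 points

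*SAP*

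**What the plan says.** SAP 10.2, item 13 ("Chronic Health Points at Screening") gives points only when the question on severe organ insufficiency or immunocompromise is answered yes. The number of points then depends on the admission classification. The table in SAP 10.2.1 has three rows:

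- "For non-operative or emergency post-operative patients": 5 points
- "For elective post-operative patients": 2 points
- "None selected": 0 points

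The text of item 13 states the last row as a rule: "If in this scenario none of these conditions is selected the Chronic Health points will be set to 0". A participant answered no also receives no points.

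The item is taken at screening, so one value enters the APACHE II score at every visit. Baseline APACHE II is the covariate in the primary ANCOVA (SAP 6.1.3). The Day 15 or discharge score is the primary outcome, and deaths by Day 15 receive the highest score observed in the trial (SAP 6.1.9). For PD analysis set 2, SAP Section 4 says: "Exclude participants with APACHE II score less than 10 at baseline programmatically". That set is used for the sensitivity analysis of the primary endpoint (SAP 6.1.4).

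**The concern.** A yes with a blank class is incomplete information about a condition that is known to be present. None of the three classes that could have been ticked leads to 0. The rule nevertheless gives this participant the same value as one without the condition, so the score is too low whichever class is true.

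This departs from how the SAP treats other gaps. Missing age is filled from the stratification factor, and most other parameters are carried forward for up to 4 days (SAP 6.1.7). SAP 10.2 leaves the total missing if an item is missing and defers imputation to the analysis datasets. Setting the item to 0 bypasses that step, because nothing then appears to be missing. The closest parallel is missing acute renal failure status, where creatinine is scored without it. There the condition itself is unknown, whereas here it has been recorded as present.

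At stake are the affected participant's baseline covariate, usually the primary score, and possibly membership of PD analysis set 2.

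**Working it through.** **Planned figure.** Protocol 12.9.1 gives 60 per arm, a difference of 3.6, SD 9.2, one-sided alpha 10% and power 80%.

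- Standard error = 9.2 × √(2/60) = 1.680.
- Power = Φ(3.6/1.680 − 1.282) = Φ(0.86) = 80.6%. The required size is 59 per arm. The plan's figure is reproduced, and it does not depend on this scoring item.

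**Points lost per affected participant.** Non-operative or emergency: 5 − 0 = 5. Elective: 2 − 0 = 2.

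**PD analysis set 2 cut-off (below 10), if the derived score is used.**

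- 5 points lost: true baselines of 10, 11, 12, 13 and 14 become 5 to 9 and fall below the cut-off.
- 2 points lost: true baselines of 10 and 11 become 8 and 9.

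**Net error in the primary ANCOVA.** For an affected participant alive at Day 15, baseline and outcome are both low by the same amount s. With baseline slope b (assumed; not in the documents), the error left after adjustment is s × (1 − b).

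| b (assumed) | s = 5: net error | per affected survivor, ÷ 60 | s = 2: net error | ÷ 60 |
|---|---|---|---|---|
| 0.3 | 3.5 | 0.058 | 1.4 | 0.023 |
| 0.5 | 2.5 | 0.042 | 1.0 | 0.017 |
| 0.7 | 1.5 | 0.025 | 0.6 | 0.010 |

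**Several affected, all in one arm of 60 (assumed worst case), s = 5.** The shift in the treatment difference is 5k(1 − b)/60.

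- k = 3: 0.175 (b = 0.3), 0.125 (b = 0.5), 0.05 (b = 0.8).
- k = 6: 0.35, 0.25 and 0.10 for the same slopes.

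**Affected participants spread evenly over the arms.** The expected shift is 0 and only noise is added. With 10% affected (assumed) and no baseline adjustment, SD = √(9.2² + 0.1 × 0.9 × 5²) = 9.32 and power is 79.8%.

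**Deaths by Day 15.** The participant's own score is replaced by the trial maximum, so the outcome is unchanged unless an affected participant holds that maximum. The baseline covariate is still too low.

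**The case against.** The strongest reply is that this is an explicit default, stated consistently in the text and the table, and that it needs two uncommon things at once: a yes answer and a blank class. Protocol 5.2 excludes eGFR of 30 or below, Child-Pugh C and recent anti-rejection or immunomodulatory drugs, which narrows the routes to a yes, although chronic lung and cardiovascular disease remain. Protocol 11.2 provides for queries on missing values, and 11.3 requires full verification of data used for primary variables. The rule is the same in both arms and the item is fixed before randomization. All of this stands, and it limits the likely impact. It does not make 0 a sensible value for a condition recorded as present. The table row is not independent support either: a no answer creates no record, so that row can only restate the same rule.

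Three stronger readings are tempting and should not be drawn.

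- A reader might infer that 0 is a value the scale never assigns. The SAP's own table lists it, and the published scale cannot be checked from these documents. What they show is that no actual admission class gives 0 after a yes.
- A reader might infer that every affected primary score is 5 points low. The loss is 2 points if the class is elective, and deaths by Day 15 take the trial maximum.
- A reader might infer that valid participants will be dropped from PD analysis set 2. Protocol 8.3.2 has the baseline score recorded on the CRF, and SAP Section 4 does not say whether the cut-off uses that score or the derived one. Exclusion is possible, not shown.

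The reply also questions 5 as a default. Protocol 5.1, criterion 4 ("Hospitalized with COVID-19-induced pneumonia evidenced by chest x-ray") does not state the reason for admission or rule out post-operative inpatients. That is correct, and it is why a query should come first. A medical admission is still by far the likeliest class.

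**Conclusion.** The point holds as a minor scoring error. A yes with a blank class gets 0, although every actual class gives 5 or 2. The participant's baseline score is too low by that amount, as is, usually, the primary score if alive at Day 15. A wrongful exclusion from PD analysis set 2 is conditional on the cut-off using the derived score, and it would touch only a sensitivity analysis. The primary analysis uses the safety set, which has no APACHE II threshold.

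The effect on the treatment difference is likely small: about 0.03 to 0.06 points per affected survivor in an arm of 60 for a 5-point loss, set against 3.6. This rests on assumed slopes of 0.7 to 0.3. The documents do not say how often the class will be blank. No arm-specific bias is expected, so they do not support a claim that the trial's conclusion depends on this rule.

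**What to change.** 1. Query every blank admission class where the chronic-health answer is yes, before database lock, and confirm the yes itself in the same query.
2. If the class is still blank, assign 5 points (non-operative), with the reason given that participants are hospitalized with COVID-19 pneumonia. Change the sentence in item 13 and the "None selected" row in SAP 10.2.1 to match.
3. State in SAP Section 4 whether the derived or the CRF baseline score drives the PD analysis set 2 cut-off.

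The cost is one changed sentence, one table row, one added sentence and a few data queries. The downside is over-scoring where the blank cannot be resolved: by 5 − 2 = 3 points for an elective post-operative participant, and by 5 points if the yes was entered in error. Either could lift a participant truly below 10 over the derived-score cut-off. Reporting the number of defaulted values by arm would show whether this matters.

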10.2.1 APACHE II Scoring

Temperature (°C)

RSORRES	RSSTRESC	RSSTRESN
>=41	4	4
39-40.9	3	3
38.5-38.9	1	1
36-38.4	0	0
34-35.9	1	1
32-33.9	2	2
30-31.9	3	3
≤29.9	4	4

Mean Arterial Pressure (mmHg)

RSORRES	RSSTRESC	RSSTRESN
>=160	4	4
130-159	3	3
110-129	2	2
70-109	0	0
50-69	2	2
≤49	4	4

Heart rate (BEATS/MIN)

Does the participant have a pacemaker?	RSORRES	RSSTRESC	RSSTRESN
Irrespective	>=180	4	4
Irrespective	140-179	3	3
Irrespective	110-139	2	2
No/unknown	70-109	0	0
No/unknown	55-69	2	2
No/unknown	40-54	3	3
No/unknown	≤39	4	4
Yes	≤109	0	0

Respiratory rate (BREATHS/MIN)

Note: Ventilated or non-ventilated patient scores will be the same as per table below

RSORRES	RSSTRESC	RSSTRESN
>=50	4	4
35-49	3	3
25-34	1	1
12-24	0	0
10-11	1	1

6-9	2	2
<=5	4	4

Impute the unit for respiratory rate as breaths/min in case it is missing.Oxygenation:

- If $\text{FiO}_2 \geq 0.5$ then use A-aDO₂ (mmHg)

RSORRES	RSSTRESC	RSSTRESN
>=500	4	4
350-499	3	3
200-349	2	2
<200	0	0

- If $\text{FiO}_2 < 0.5$ then use PaO₂ (mmHg)

RSORRES	RSSTRESC	RSSTRESN
>70	0	0
61-70	1	1
55-60	3	3
<55	4	4

If any value for <X, impute the value X in that case.

Arterial pH

- Use arterial pH if reported

RSORRES	RSSTRESC	RSSTRESN
>=7.7	4	4
7.6-7.69	3	3
7.5-7.59	1	1
7.33-7.49	0	0
7.25-7.32	2	2
7.15-7.24	3	3
<7.15	4	4

- Alternatively use Serum HCO₃ (mmol/L)

RSORRES	RSSTRESC	RSSTRESN
>=52	4	4
41-51.9	3	3
32-40.9	1	1
22-31.9	0	0
18-21.9	2	2
15-17.9	3	3
<15	4	4

Serum sodium (mmol/L)

RSORRES	RSSTRESC	RSSTRESN
>=180	4	4
160-179	3	3
155-159	2	2
150-154	1	1
130-149	0	0
120-129	2	2
111-119	3	3
<=110	4	4

Serum potassium (mmol/L)

RSORRES	RSSTRESC	RSSTRESN
>=7	4	4
6-6.9	3	3
5.5-5.9	1	1
3.5-5.4	0	0
3-3.4	1	1
2.5-2.9	2	2
<2.5	4	4

Serum creatinine (mg/dL)

RSORRES	RSSTRESC	RSSTRESN
>=3.5 and acute renal failure ="yes"	8	8
2-3.4 and acute renal failure ="yes"	6	6
1.5-1.9 and acute renal failure="yes"	4	4
0.6-1.4 and acute renal failure ="yes"	0	0
<0.6 and acute renal failure ="yes"	4	4
>=3.5	4	4
2-3.4	3	3
1.5-1.9	2	2
0.6-1.4	0	0
<0.6	2	2

Hematocrit (%)

RSORRES	RSSTRESC	RSSTRESN
>=60	4	4
50-59.9	2	2

46-49.9	1	1
30-45.9	0	0
20-29.9	2	2
<20	4	4

White Blood Count ($10^9/L$)

RSORRES	RSSTRESC	RSSTRESN
≥ 40	4	4
20-39.9	2	2
15-19.9	1	1
3-14.9	0	0
1-2.9	2	2
<1	4	4

Age points (years)

RSORRES	RSSTRESC	RSSTRESN
≤ 44	0	0
45-54	2	2
55-64	3	3
65-74	5	5
≥ 75	6	6

Chronic health points

RSORRES	RSSTRESC	RSSTRESN
For non-operative or emergency post-operative patients	5	5
For elective post-operative patients	2	2
None selected	0	0

Commercially Confidential Information

10.5 Glasgow Coma Score

10.5.1 Glasgow Coma Scoring

- Best eye response

Result	Score (Char)	Score (Num)
No eye opening	1	1
Eye opening to pain	2	2
Eye opening to verbal command	3	3
Eyes open spontaneously	4	4
Untestable	Untestable	
Unknown	Unknown	

- Motor response

Result	Score (Char)	Score (Num)
No motor response	1	1
Abnormal extension	2	2
Abnormal flexion	3	3
Flexion withdrawal	4	4
Localizes pain	5	5
Obeys command	6	6
Untestable	Untestable	
Unknown	Unknown	

- Verbal response

Result	Score (Char)	Score (Num)
No verbal response	1	1
Incomprehensible sound	2	2
Inappropriate words	3	3
Confused	4	4
Oriented	5	5
Untestable	Untestable	
Unknown	Unknown	

10.6 9-point ordinal scale

Patient State	Descriptor	Score	Abbreviated description
Uninfected	No Clinical or virological evidence of infection	0	Uninfected
Ambulatory	No limitation of activities	1	Amb: No limitations
	Limitation of activities	2	Amb: Limitations
Hospitalized Mild disease	Hospitalized, no oxygen therapy	3	Hosp: No Oxygen
	Oxygen by mask or nasal prongs	4	Hosp: Oxy Mask/ Nasal prongs
Hospitalized Severe disease	Non-invasive ventilation or high-flow oxygen	5	Hosp: Non-Inv Vent/ High flow oxy
	Intubation and mechanical ventilation	6	Hosp: Intub + Mech Vent
	Ventilation + additional organ support - pressors, RRT, ECMO	7	Hosp: Vent + pressors
Dead	Death	8	Dead

10.7 Steroid conversion factors

Steroids will be displayed using prednisone equivalent doses. The doses displayed in the following table are considered equivalent. To determine prednisone equivalent doses, doses (in unit mg) will be multiplied by the conversion factor shown in [Table 10-2](#). In case multiple corticosteroids are used at a certain visit the prednisone equivalent doses will be added up to obtain the total prednisone equivalent dose.

Table 10-2 Steroids conversion factors

WHO drug code	Preferred Term Corticosteroid	Equivalent Dose [mg]	Conversion Factor
000447xx	Prednisone	5	1
000162xx	Prednisolone	5	1
000496xx	Methylprednisolone	4	1.25
012428xx	Meprednisone	4	1.25
001867xx	Prednylidene	5 5/7	0.875
000319xx	Triamcinolone	4	1.25
000146xx	Cortisone	25	0.2
000286xx	Hydrocortisone	20	0.25
002131xx	Fludrocortisone	2	2.5
000085xx	Betamethasone	0.75	20/3
000664xx	Paramethasone	2	2.5
000160xx	Dexamethasone	0.75	20/3
008827xx	Deflazacort	6	5/6

Commercially Confidential Information

Commercially Confidential Information
